Ketamine has shown early evidence of efficacy in the treatment of substance use disorders. One study evaluating the adjunctive use of ketamine in heroin use disorder showed that a single-session of highdose (2 mg/kg IM) ketamine demonstrated one-month abstinence rates of 85% compared to 55% abstinence in the low dose group (0.2 mg/kg IM), and one-year abstinence rates of 24% in the high dose group as compared to 6% in the low-dose control group (Krupitsky et al., 2002). In a follow-up study comparing three repeated sessions of ketamine infusions with concurrent psychotherapy to single-session treatment, abstinence rates were increased to 50% in the 3 session group as compared to the single session rate of 22% (Krupitsky et al., 2007). Related studies found that ketamine is useful as an adjunct to psychotherapy in the treatment of alcohol use disorder (Krupitsky and Grinenko, 1997) with one-year complete abstinence rates of 65.8% in the ketamine-assisted psychotherapy group compared to 24% in the control psychotherapy group. Intriguingly, the anti-depressant response to ketamine occurs primarily after the drug has been cleared from the body, suggesting that its primary effects are mediated through downstream processes. Ketamine has also been shown in a randomized controlled trial to facilitate rapid-opioid induction under general anesthesia, with significant improvements in clinical and subjective opioid withdrawal symptoms (Jovaisa et. al., 2006). More recently, ketamine has been studied in cocaine use disorder and found to improve levels of motivation to quit using and to reduce cocaine craving (Dakwar et al., 2014) and reduce rates of cocaine self-administration by 67% relative to baseline (Dakwar et al., 2017; Dakwar et al., 2018). Ketamine has been studied as an adjunct agent to benzodiazepines for acute alcohol withdrawal and has been found to reduce supplementary diazepam equivalent requirements by 40 mg at 12 hours post-ketamine initiation while maintaining equivalent levels of withdrawal symptoms between groups (Wong et al., 2015).

Novelty and Importance of the Current Study

While non-controlled trials for heroin and small pilot trials for other substance of abuse have shown evidence that ketamine improves abstinence rates and motivation to quit while reducing cravings, there are no completed randomized controlled trials evaluating the efficacy of ketamine in increasing abstinence in OUD.

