4.3 Exploratory Outcomes

Exploratory outcomes will include changes in characteristics related to opioid addiction including percentage of days using opioids and abstinence rates (Timeline Followback), motivation to quit (University of Rhode Island Change Assessment), craving for opioids (Visual Analog Scale), and related areas of psychiatric functioning.

- Timeline Follow-Back (TLFB; Sobell & Sobell, 1992): The TLFB obtains retrospective self-report of substance use by using a calendar and memory prompts to stimulate recall. Quantity and frequency assessments are made using this instrument (e.g., total amount of opioids used, percent of days using) as well as abstinence (yes/no). TLFB yields consistently high test-retest correlations and correlates well with other self-reports and collateral reports. The TLFB will assess consumption of opioids for 60 days prior to study entry, during the interventional phase and the follow-up phase. Use of nicotine and other drugs of abuse, including prescription drugs, will also be assessed using the TLFB.
- Urine Drug Screen (UDS) tests: Urine samples will be tested with a Multi-Drug Panel Test, which allows for the detection of THC/Marijuana, Cocaine, Phencyclidine, Opioids, Methamphetamines, Amphetamines, Barbiturates, and Benzodiazepines.
- Saliva Drug Screen tests: For follow-up visits conducted by telehealth, a Multi-Drug Panel saliva drug screen test may be optionally used in place of urine tests to facilitate ease of testing in a home setting.
- University of Rhode Island Change Assessment Scale (URICA; DiClemente & Hughes, 1999): This 32-item, self-reported questionnaire uses a five point Likert scale to assess levels of motivation to change according to the transtheoretical model (Precontemplation, Contemplation, Action, and Maintenance). This will be measured as the level of motivation to make changes may be mechanistically related to improving in opioid use.
- Visual Analog Craving Scale (VAS; McMillan & Gilmore-Thomas, 1996). At baseline, during the interventional visits, and at each follow-up visit, patients will be asked to report on the frequency, duration, and intensity of their opioid cravings on a 10 point (100 mm) VAS. This approach has been shown to yield a reliable and valid measure of craving in previous research.

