10.5 Method and Administration of Randomization

Randomized permuted blocks will be employed to obtain balanced randomization sequences for the two groups. The PI will be blinded to the randomization sequence and communicated to a designated pharmacist who not involved in clinical management of participants in order to preserve the double-blind design. The randomization assignment of participants will be carried out by this pharmacist

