12.2 Hypotheses for Analyses

Feasibility Hypothesis: From the cohort of individuals completing the initial prescreening assessment, a 75% study enrollment rate will be deemed feasible. Therefore, we anticipate that 40 individuals will be needed to complete prescreening so that 30 participants will enroll in the study. Of the individuals enrolling in the study, we anticipate 60% of participants will *complete* the study protocol. *Completion* is defined for the study purposes as completing at least 75% of the study visits.

Hypothesis 1: Ketamine will result in significantly greater reduction in depression symptoms as compared to placebo at one-month. To test this hypothesis, we will employ repeated measures ANOVA using linear mixed models approach to assess reduction on the total score of the MADRS.

Hypothesis 2: Ketamine will result in significantly greater reduction in frequency of opioid use as compared to placebo at one-month. To test this hypothesis, we will treat the percent days using opioids (TLFB) as a continuous variable and analyze using linear mixed models approach. Abstinence at one-week (on UDS) will be compared by intervention groups using logistical regression analyses. An arcsine square root or logit transformation may be considered to stabilize variance of the proportions.

Hypothesis 3: Response to ketamine will be influenced by changes in motivation to quit (URICA) and qualities of psychoactive perceptual experience (HMS). To test this hypothesis, we will employ repeated measures ANOVA using linear mixed models approach.

Alternate Approaches: Diagnostics of the residuals will be performed to test the assumptions of the analysis. If the assumptions are found to be inadequate, alternative methods of analysis (e.g. ordinal logistic regression or Poisson regression) will be considered.

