The primary dependent variables in all three analyses will be intervention group (ketamine or placebo), time (number of days), and the interaction between the two. Main hypothesis of interest will be the interaction and the post-hoc comparison at the one month after the first intervention. We anticipate the study population to include participants that are currently on antidepressants as well as those that are not. We considered stratifying randomization by this variable, however since the proporption of participants on antidepressants at baseline is expected to be small, this will be considered as an independent variable in the statistical analysis. To account for within subject correlations, several structures, such as spatial autocorrelation (to accommodate unequal time points), and AR(1) symmetry, will be examined. Diagnostics will be considered. An arcsine square root transformation may be considered to stabilize variance of the proportions. In all of the analyses, covariates will be considered to examine mediations. In a secondary analysis based on the spaghetti plots, we will consider linear and non-linear models of outcomes as a function of time. Specifically, over the 8-week follow-up period, we will examine if there exists a threshold point in time where the effect of ketamine plateaus. To achieve this, treating the joint-point as unknown, we will fit segmented regression models using non-linear mixed models.

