12.3 Justification of Sample Size

PROTOCOL TITLE: Ketamine for the Treatment of Opioid Use and Depression Version Date: December 20, 2021

For a 75% anticipated enrollment rate from the initial prescreened sample of 40 individuals, feasibility can be estimated within a margin of error of 14% with 95% confidence. Similarly, assuming a 60% rate of study enrollment of eligible participants, with a sample size of 30 we can estimate feasibility within a 17% margin of error with a 95% confidence interval. This study is powered to estimate the effects of ketamine on significant reduction in MADRS symptoms at the end of one month (see Hypothesis 1). Over the course of a two-year study, we estimate that we will be able to recruit 15 patients in each of the two intervention arms (2/month over 15 months). At 80% power, this sample size will allow us to detect a minimum difference in MADRS scores of 14.4 at one month between the ketamine and the placebo groups in a study design with 7 repeated measurements having a AR(1) correlation of 0.9, and a standard deviation of 15.8, with a significance level of 0.050 (Singh et al., 2016; Niciu et al., 2014). While we will examine changes in depression severity as a continuous variable, we will also examine other clinically accepted changes in depression severity such as response (defined as a 50% reduction in symptom severity from baseline) and remission (defined as below the threshold for mild depression which is a score of 6 on the MADRS). Baseline averages for the MADRS scores for this population will be assumed to be 34 (Niciu et al., 2014; Han et al., 2016; Singh et al., 2016). The minimum difference in MADRS of 14.4 is anticipated to be approximately 50% of the baseline measurements. Although there is limited information on the effectiveness of ketamine in the treatment of addiction, a sample of 30 subjects (15 in each arm) will provide adequate power to detect an 22% difference between the two groups in the percent of days abstinent from opioid use using the same longitudinal design as described above with 7 time points (Hypothesis 2). For this calculation, we assumed an AR(1) correlation of 0.9 and a standard deviation of 25% at a significance level of 0.05; an arcsine transformation was used for variance stabilization. Over the 8-week follow-up period, we will examine if there exists a threshold point in time where the effect of ketamine plateaus. To achieve this, we will use a segmented regression analysis using non-linear mixed models. We will take all efforts to keep dropouts to a minimum. However, our past experience suggests the rates of dropout are up to 20%. This could reduce the sample size per group to 12 and 12. The corresponding differences we could detect would be a minimum MADRS score difference of 16.1 and a 26% difference between groups in terms of the percent of days abstinent from opioid use. No interim analyses are planned.

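### The one-week abstinence comparison uses logistic regression with 15 per arm but names no test statistic and no method that survives an empty cell

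*Combined protocol and SAP*

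**What the plan says.** Under Hypothesis 2, section 12.2 says: "Abstinence at one-week (on UDS) will be compared by intervention groups using logistical regression analyses". It does not say whether the p-value is a Wald, likelihood-ratio or exact one, and it gives no rule for sparse tables.

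- **Fallback.** The alternative approaches in 12.2 are triggered by residual diagnostics, with ordinal logistic and Poisson regression as examples. The arcsine and logit transformations are there to stabilise the variance of proportions. None of these deals with an empty cell.
- **Size.** Section 12.3 says that "a sample of 30 subjects (15 in each arm) will provide adequate power to detect an 22% difference". That figure concerns percent of days abstinent, a continuous measure. On dropout it adds: "This could reduce the sample size per group to 12 and 12". No power is stated for the binary comparison.
- **Allocation.** Section 10.5: "Randomized permuted blocks will be employed to obtain balanced randomization sequences for the two groups".
- **Rank.** Section 4.3 places "percentage of days using opioids and abstinence rates (Timeline Followback" and the drug screen among the exploratory outcomes. Specific Aim 2 also names abstinence, and Table 2 calls the drug screen a secondary outcome measure.
- **Covariates.** Section 12.2 says of baseline antidepressant use, expected to be uncommon, that "this will be considered as an independent variable in the statistical analysis".

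**The concern.** With about 30 binary results, an arm can end with none or all of its participants abstinent. Maximum likelihood then has no finite odds ratio. Software stops at a large coefficient with a huge standard error, and the Wald test that most packages print returns p near 1. The analysis would give no usable answer in a table where one arm has clearly done better. This is the only stated analysis of the drug screen, the trial's objective opioid measure.

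Leaving the statistic open does not solve this. The analyst could turn to the likelihood-ratio test from the same fit, but that test rejects too often at this size. Choosing between the two after seeing the table would be data-driven.

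**Working it through.** **1. The plan's own design figure.** The nearest stated figure is the MADRS detectable difference, with seven measurements "having a AR(1) correlation of 0.9, and a standard deviation of 15.8, with a significance level of 0.050" (12.3). The variance factor is the mean of the 7 × 7 matrix 0.9^|i−j|, which is 0.798. The detectable difference is (1.960 + 0.842) × SD × √(2 × 0.798/n).

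- n = 15: 2.802 × 15.8 × √0.1064 = 14.44 (stated 14.4).
- n = 12: 2.802 × 15.8 × √0.1330 = 16.14 (stated 16.1).

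The percent-days figures come to 22.8 and 25.5 before the arcsine step (stated 22 and 26). So 15 or 12 per arm at two-sided 0.05 is the plan's working basis. I use it below, although the plan does not state sidedness.

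**2. One table, 5/15 v 0/15.**

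- *Wald.* The log odds ratio is ln[a(n−b)/(b(n−a))], with a = 5 and b = 0, so it is undefined. A fitted model stops at about 21.9 with SE about 12,444. Then z = 21.9/12,444 = 0.0018 and p = 0.9986.
- *Ordinary likelihood ratio.* The common rate is 5/30 = 0.167. 2[5 ln(0.333/0.167) + 10 ln(0.667/0.833) + 15 ln(1/0.833)] = 7.94, p = 0.005.
- *Firth.* In a 2 × 2 table the penalty adds ½ to each cell. The rates are 5.5/16 = 0.344 and 0.5/16 = 0.031, and the common rate is 6/32 = 0.1875. 2[5.5 ln(0.344/0.1875) + 10.5 ln(0.656/0.8125) + 0.5 ln(0.031/0.1875) + 15.5 ln(0.969/0.8125)] = 5.84, p = 0.016. The odds ratio is finite: (5.5 × 15.5)/(0.5 × 10.5) = 16.2.
- *Fisher's exact test.* p = 0.042.

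**3. Rates.** The documents give no expected one-week abstinence rate. The Background cites "one-month abstinence rates of 85% compared to 55% abstinence in the low dose group", 24% v 6% at one year in the same study, and 50% v 22% in a follow-up study of repeated against single sessions. These come from other comparisons at other times and serve only as illustrations.

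**4. Chance of an empty cell.** P = 1 − [1 − p₁ⁿ − (1−p₁)ⁿ][1 − p₂ⁿ − (1−p₂)ⁿ]. For 24% v 6% at n = 15: 0.76¹⁵ = 0.016 and 0.94¹⁵ = 0.395, so P = 1 − 0.984 × 0.605 = 0.405. For 85% v 55% nearly all of it is 0.85¹⁵ = 0.087. For 50% v 22% it is 0.78¹⁵ = 0.024.

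**5. Power.** Every possible table was weighted by Bin(a; n, p₁) × Bin(b; n, p₂), and the weights of tables with p ≤ 0.05 were added. Wald p was set to 1 where a cell is empty.

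| Rates | n per arm | Empty cell | Wald | Firth | Fisher |
|---|---|---|---|---|---|
| 50% v 22% | 15 | 2% | 28.6% | 32.5% | 20.7% |
| 85% v 55% | 15 | 9% | 27.5% | 40.3% | 27.5% |
| 24% v 6% | 15 | 41% | 2.0% | 24.9% | 12.9% |
| 50% v 22% | 12 | 5% | 27.0% | 31.7% | 18.1% |
| 85% v 55% | 12 | 14% | 24.1% | 36.4% | 21.7% |
| 24% v 6% | 12 | 50% | 1.8% | 17.1% | 7.0% |

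At 15 per arm, the empty-cell tables that Firth calls significant carry probability 0.024, 0.084 and 0.199 (rows in order), out of total gains of 0.039, 0.128 and 0.229. The rest of each gain comes from one pattern, 6/15 v 1/15 and its mirror images (Wald p = 0.054, Firth p = 0.036).

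**6. Type I error.** The same sum was taken with p₁ = p₂, over common rates from 1% to 99%.

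- 15 per arm: ordinary likelihood ratio up to 8.2% (7.8% at a common rate of 10%); Firth at most 4.3%. Firth rejects every table that Wald rejects.
- 12 per arm: Firth up to 6.4%, Wald up to 6.3%. Boschloo's test keeps its level by construction. The same enumeration gives it power of 27.8%, 34.9% and 17.1% for the three pairs, in table order.

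**The case against.** The strongest reply is that the plan never specifies a Wald test. That is correct. The likelihood-ratio test from the same model would detect 5/15 v 0/15, and at 85% v 55% its power is 46%. But that test exceeds its nominal level at 15 per arm, and the odds ratio is infinite whichever test is used. The point therefore stands as one about pre-specification.

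The outcome is also exploratory: the primary outcomes are feasibility, and the lead analysis under Hypothesis 2 is percent days of use. This lowers the weight of the point without removing it.

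A reader might infer more than the documents support:

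- *That an empty cell is likely, because everyone used illicit opioids in the month before entry.* Section 5.2 requires one such use, in people already on OUD pharmacotherapy. That does not imply a one-week negative-screen rate near zero, and the chance at the cited rates runs from 2% to 41%.
- *That Wald is very conservative even without an empty cell.* At 15 per arm it differs from Firth in only one non-empty pattern, and at a common rate of 55% both have type I error of about 4.2%.
- *That 85% v 55% is a planning assumption.* It is a cited background result.
- *That any exact test would help.* Fisher's test has less power than Wald at 50% v 22%.
- *That abstinence is defined in two conflicting ways, by TLFB in 4.3 and by drug screen in 12.2.* Section 1.4 names both instruments, which can be read as complementary. A composite would be a preference, not a correction.
- *That antidepressant use enters this model.* The sentence sits with the models of group, time and their interaction, so applying it here is an inference. If it did enter, sparse cells would be more of a problem than the unadjusted figures show.

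**Conclusion.** The point holds as a gap in pre-specification for an exploratory outcome. Section 12.2 names logistic regression for arms of 15, possibly 12, without a test statistic or a method that remains usable with an empty cell, and its fallback does not supply one. Of the two ordinary readings, Wald gives no usable result in such a table and the likelihood-ratio test reaches 8.2% type I error. At 15 per arm Firth is at least as powerful as Wald for every pair of rates and stays within 4.3%.

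The gain over Wald is about 4, 13 and 23 percentage points at the three cited pairs. It is large only when one arm is near 0% or 100%. Even with Firth, power at these rates is at most 40%, so most such differences would be missed by any of the level-keeping methods. Small sample size is the main limit, and a change of method does not alter that.

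These figures assume two-sided 0.05, a drug-screen result for every counted participant, no covariates, and background rates used only as illustrations.

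**What to change.** In 12.2, replace the abstinence sentence with text to this effect: *Abstinence on the one-week drug screen will be compared by Firth-penalised logistic regression with treatment as the main term, tested by the penalised likelihood ratio, with a profile-likelihood interval for the odds ratio. The risk difference will be reported with a small-sample interval.* Name the interval method.

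Boschloo's exact test is an acceptable alternative. It is the stricter choice if the arms fall to 12, where Firth's maximum size is 6.4%, at the price of somewhat lower power at two of the three pairs of rates. It takes no covariates, so Firth is the better fit if adjustment is wanted. Choose one before unblinding.

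The cost is a few sentences of analysis text. Both methods are in standard software. The penalised odds ratio is slightly shrunk toward 1, which should be noted when it is reported.

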1.3 Purpose and Objectives of the Study

The primary objective of the proposed study is to directly address this critical need by preliminarily testing the efficacy of ketamine in reducing opioid use and depression symptoms among individuals (N=30) with concurrent OUD and MDD who have failed to maintain abstinence despite treatment with a standard of care pharmacotherapy for OUD (i.e. buprenorphine, methadone or naltrexone). Effects on related symptoms and psychiatric conditions (e.g., cravings, motivation to quit, and anxiety symptoms) will also be explored. To accomplish this, we will use an intent-to-treat, double-blind, randomized clinical trial to compare the efficacy of ketamine to placebo control over a twice-weekly treatment schedule for four weeks. We will examine standardized, repeated dependent measures of clinical outcomes at baseline and multiple time points after the first treatment (48h to 8 weeks post initial treatment) with primary outcomes assessed at one month following the first treatment.

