1.4 Specific Aims

To achieve these objectives, the following Specific Aims are proposed:

Specific Aim 1: To demonstrate the feasibility of study recruitment and completion of the treatment protocol.

Specific Aim 2: To preliminarily assess the efficacy of ketamine, as compared to placebo, in reducing OUD severity (i.e., percent days using opioids, abstinence rates) as measured by the Timeline Followback and urine drug screen tests.

Specific Aim 3: To preliminarily assess the efficacy of ketamine, as compared to placebo, in reducing symptoms of depression using the Montgomery–Asberg Depression Rating Scale.

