12.0 DATA MANAGEMENT

12.1 Data Analysis Plan

Baseline demographic characteristics will be collected and descriptive statistics will be used to characterize participants. Data will be collected and managed using the secure REDCap (Research Electronic Data Capture) database. Descriptive statistics for primary outcomes will include 1) the percentage of individuals completing informed consent out of the number of individuals eligible on the

initial screening and 2) the percentage of individuals that complete informed consent which complete the full protocol. Other descriptive statistics for the sample population will be analyzed, and baseline characteristics that are found to be significantly associated with other outcome measures will be included as covariates. Spaghetti plots will be produced to guide modeling outcomes as a function of time. All analyses will be conducted based on intention to treat. Subjects assigned to Group B (placebo) who complete Study Wk4 (at which time main outcomes are assessed), may choose to receive 8 ketamine treatments before completing follow-up visits. To preserve study blinding, subjects who are among the final 6 subjects being enrolled will not be unblinded until primary outcomes are assessed for all 30 subjects.

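### Hypothesis 2 is set at one month, but the only specified urine-abstinence test is at an undefined one week, so self-reported opioid use has no objective comparison at the Week 4 assessment

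*Combined protocol and SAP*

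**What the plan says.** Section 12.2 words Hypothesis 2 as "Ketamine will result in significantly greater reduction in frequency of opioid use as compared to placebo at one-month". The test named for it is on the Timeline Followback (TLFB): "we will treat the percent days using opioids (TLFB) as a continuous variable and analyze using linear mixed models approach". The next sentence brings in the urine result: "Abstinence at one-week (on UDS) will be compared by intervention groups using logistical regression analyses". It gives no starting point for the week, and no other section specifies a UDS comparison at any other time.

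Elsewhere the document points to one month:

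- Section 1.3: "with primary outcomes assessed at one month following the first treatment".
- Section 12.1, on placebo participants who may go on to ketamine, refers to those who "complete Study Wk4 (at which time main outcomes are assessed".
- Section 12.2, after the hypotheses: "Main hypothesis of interest will be the interaction and the post-hoc comparison at the one month after the first intervention".
- Section 1.4, Aim 2, names both instruments: "percent days using opioids, abstinence rates) as measured by the Timeline Followback and urine drug screen tests".

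On the status of these measures, section 4.3 says "The TLFB obtains retrospective self-report of substance use" and lists the opioid outcomes as exploratory. Table 2 classes the drug screen as a secondary outcome. Section 4.1 makes feasibility the primary outcome.

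**The concern.** Hypothesis and urine test stand side by side in one paragraph with different time points. TLFB is self-report. The urine screen is the only objective opioid measure, because the saliva test in section 4.3 is only an optional substitute for it at telehealth follow-up. If the plan is followed as written, a group difference in self-reported use at one month has no specified objective result beside it at that time.

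The undefined week adds a second problem. Two analysts could take the same sentence and analyse visits about a month apart, one early in treatment and one after it. In a 30-participant trial, that choice should not remain open until the data are seen.

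**Working it through.** **1. Where one week falls.** Inputs: the visit layout in section 10.1 (two treatments per week in Study Weeks 1 to 4, then the one-week follow-up or the first optional ketamine session in Week 5), the column heads of Table 2, and section 10.6, which places urine testing before each injection.

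| Reading | Visit | Doses before the screen | Relation to Week 4 |
|---|---|---|---|
| One week after first treatment, next visit | Tx3, Week 2 | 2 of 8 (25%) | about two weeks before |
| Same, nearest screen within Week 1 | Tx2 | 1 of 8 (12.5%) | about three weeks before |
| One-week follow-up, no crossover | Week 5 | 8 of 8 | one week after |
| One-week follow-up, placebo crossover | Week 9 | 8 placebo, then 8 ketamine | five weeks after |

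Sections 1.3 and 12.2 both count one month from the first treatment. The first two rows therefore follow the plan's own convention.

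On the follow-up reading, Week 5 − Week 1 = 4 weeks, which is about one month after the first injection. It is still after the Week 4 assessment. By then placebo participants may know their assignment and be starting open ketamine; section 12.1 holds back unblinding only for the final 6 enrolled. If visits are matched by label, the crossover participants contribute Week 9, after eight ketamine sessions. That is no longer ketamine against placebo.

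**2. Which screens exist.** The drug-screen row of Table 2 carries 11 marks, consistent with Tx1 to Tx8 plus three follow-ups. Tx1 is taken before the first dose, so it is a baseline value. The three follow-ups fall in or after the optional crossover period. Randomised post-dose screens: 11 − 1 − 3 = 7, namely Tx2 to Tx8. Tx8 is in Week 4; being pre-dose, it reflects seven doses.

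**3. Whether the general text fills the gap.** The paragraph after the hypotheses describes group, time and their interaction, with a one-month contrast. A logistic regression at one visit has no time term and no interaction, so that paragraph does not turn the one-week comparison into a one-month one.

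**4. Numbers.** Section 12.3 has no calculation for binary UDS abstinence. Its nearest figure is a detectable difference of 22% in percent days abstinent with 15 per arm (26% with 12). For the mean of 7 measurements with AR(1) correlation 0.9, the variance factor is Σ0.9^|i−j|/49 = 0.798, and the detectable difference is (1.960 + 0.842) × SD × √0.798 × √(2/n).

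- MADRS, SD 15.8: 14.44 (n = 15) and 16.14 (n = 12). The plan states 14.4 and 16.1.
- Percent days, SD 25: 22.8 (n = 15) and 25.5 (n = 12). The plan states 22 and 26. The plan gives neither a power for this outcome beyond calling it adequate nor the arcsine baseline, so I do not call the 22 wrong.

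For a single-visit UDS comparison, two-sided 0.05, n = 15 per arm, with p̄ = (p0 + p1)/2:

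power = Φ{[|p1 − p0| − 1.96√(2p̄(1 − p̄)/n)] / √([p0(1 − p0) + p1(1 − p1)]/n)}

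The documents give no control UDS abstinence rate, so p0 is an assumption:

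| Assumed p0 | p1 for 80% power | Difference (points) | Power for +22 points |
|---|---|---|---|
| 10% | 56.3% | 46.3 | 31% |
| 20% | 68.9% | 48.9 | 25% |
| 30% | 79.0% | 49.0 | 22% |
| 40% | 87.3% | 47.3 | 22% |
| 55% | 97.0% | 42.0 | 24% |

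These figures depend on n and the rates, not on the visit.

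**The case against.** The best defence is that UDS abstinence is a separate binary outcome and not the test of Hypothesis 2, which concerns frequency of use and is tested on TLFB. An early abstinence endpoint is a legitimate choice, the opioid outcomes are exploratory in section 4.3, and no primary conclusion depends on them. The point about status stands and limits the severity. The rest does not remove the gap: Aim 2 names UDS beside TLFB, the plan never presents one week as a deliberate early endpoint, and no later UDS comparison is specified.

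Three stronger readings that a reader might infer are not supported:

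- **That no reading comes near one month.** The Week 5 follow-up is about four weeks after the first injection. Tx8, at about 3 to 3.5 weeks, is no closer to one month by the calendar. Its advantages are that it falls in the Week 4 of section 12.1 and is the last screen before crossover.
- **That a Week 5 screen is already affected by open ketamine.** Urine is collected before dosing, so a sample at the first optional session precedes any open dose. What remains is possible knowledge of assignment, and the Week 9 problem if visits are matched by label.
- **That the plan uses 1 of 11 screens, or 9%.** That denominator includes a pre-dose screen and three follow-ups in or after the crossover period. Nor does the plan forbid other UDS analyses; it specifies only this one.

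**Conclusion.** The concern holds in this limited form. The only specified UDS abstinence comparison is at a time with no stated origin. Under the plan's own way of counting, it follows at most 2 of 8 doses. Under the other reading it falls after the main assessment, and for crossover participants it may follow eight ketamine sessions. On neither reading is there a specified objective comparison at Week 4, although the screens are scheduled.

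This should be corrected, but it does not threaten the trial. It affects the interpretation of an exploratory or secondary efficacy outcome and leaves the feasibility outcomes untouched. The gap is in the analysis, not in data collection. Moving the visit will not make the single-visit comparison informative at this sample size: a 22-point difference would have about 22% to 31% power over the assumed control rates. The conclusion rests on section 10.6 applying to every treatment visit and on the 11 marks in Table 2 falling under Tx1 to Tx8 and the three follow-ups.

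**What to change.** Replace the UDS sentence in section 12.2 with text to this effect: UDS abstinence from non-prescribed opioids at the Tx8 (Study Week 4) screen will be compared between randomised groups by logistic regression; a supportive repeated-measures logistic model will use the Tx2 to Tx8 screens, with the pre-dose Tx1 screen as a baseline covariate, and report the group contrast at Week 4. If a one-week result is wanted, define it as one week after the first treatment, name the visit, and label it early and descriptive.

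Define a negative screen in the same place. Participants take prescribed OUD pharmacotherapy, which may be methadone or buprenorphine (section 5.2), and section 4.3 describes the panel only as detecting opioids as a class. The text should say how a result explained by prescribed medication is classified and how missed screens are counted.

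The cost is a short paragraph plus that definition, with no added visits, samples or participants. It should be settled before anyone reviews outcomes by arm.
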